7.6. Sensitivity analyses

We will conduct sensitivity analyses to examine whether the pattern of results from the main analyses differ when:

- excluding the aim guessers from the main analyses, or if more than 20% of participants guess the aim of the study, including an 'aim guessing' variable (two levels: yes, no) as a covariate in the main model;
- substituting highest educational qualification by level of education (composite score) in the main model;
- including hunger and liking as covariates in the main model as these two variables are likely to influence how much one serves oneself of a dish;
- excluding any dish that is familiar to less than 50% of participants or that is scored < 50 in liking on average (mid-way of the scale) to examine whether results are consistent when only well liked and familiar foods are used.

We will report whether sensitivity analyses result in deviations from the pattern of significance to the main analyses (i.e., any significant differences between conditions becoming not significant, and vice versa).

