5.6. Familiarity and liking of the test foods

Participants will be presented with the picture of the 600 kcal portion of each food, as UK public health guidelines recommend energy consumption ≤ 600 kcal for a main meal [26], and asked:

- “Have you ever eaten this food?” Answers: yes or no (*familiarity*)
- “How much do you like this food?” Answers on a 100-point visual analogue scale (anchors: not at all, extremely) (*liking*) [21]

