6. STUDY FLOW

RECRUITMENT (Prolific)	
 ▪ Predefined screening questions of Prolific website will be used to target the sample (Appendix B) ▪ Participants who meet the inclusion/exclusion criteria will be emailed by Prolific and/or offered to complete our study on their Prolific account (Appendix C) ▪ Eligible participants who want to take part on the study will click on the start button and be redirected to our study website (Inquisit)
INFORMED CONSENT	
 ▪ Participants will read the information sheet (Appendix D) ▪ Participants who want to proceed will tick a consent box (Appendix E)
RANDOMISATION	
 ▪ Participants will be equally randomised and allocated to one of the four experimental groups using Inquisit software
BASELINE ASSESSMENTS	
 ▪ Participants will complete a baseline questionnaire on demographics (Appendix G)
MEAL CHOICE TASK	
 ▪ Instructions will be displayed (Appendix H) ▪ Meals will be displayed in randomised order

	Energy labelling (kcal+/PACE-)	PACE labelling (kcal-/PACE+)	Energy and PACE labelling (kcal+/PACE+)	No labelling (kcal-/PACE-)
EXECUTIVE FUNCTION	Tasks randomised in order: 
 ▪ Inhibition (Stroop task) ▪ Working memory (backwards digit-span task) 			
HEALTH MOTIVATION	
 ▪ Health and weight control subscales from the Food Choice Questionnaire (Appendix I) 			
PHYSICAL ACTIVITY LEVEL	
 ▪ International Physical Activity Questionnaire – Short Version (IPAQ-SF) (Appendix J) 			
FAMILIARITY AND LIKING	
 ▪ For each dish: 
 ○ Familiarity (Appendix K) ○ Liking rating (Appendix L) 			
DEBRIEFING QUESTIONNAIRE	
 ▪ Aim guessing in an open-ended response format (Appendix M) ▪ Questionnaire (Appendix M) 			
ADDITIONAL MEASURES	
 ▪ Interoception preliminary survey¹ (Appendix N) 			
DEBRIEFING TEXT	
 ▪ Tell the participants what the study was about (Appendix O) 			
DATA MANAGEMENT	
 ▪ The result files will contain: 
 ○ Participant unique ID ○ Experimental condition participant is directed to ○ Amount of self-served food ○ Answers to questionnaires 			

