Inhibition – Stroop task: The median reaction times (RTs) will be calculated for correct responses in incongruent and congruent trials. The interference effect will be calculated as the difference between the median RTs of the incongruent trials and the congruent trials. A larger interference score is indicative of poorer inhibition. RTs data are commonly skewed, reflecting lapses of attention or eye blinks during the task [28]. To resolve this, median will be used instead of means. Median is less affected by extreme scores than the mean and provides a better estimate of central tendency for skewed distributions [29], [30]. We will also calculate the proportion of correct responses in incongruent trials because this outcome has been previously linked to the frequency of fatty food consumption [31].

Working memory – backwards digit-span task: The two-error maximum length will be calculated. It is the last digit-span a participant gets correct before making two consecutive errors and the traditional measure of a participant's backward digit span [32]. We will also calculate the maximum length i.e., the maximal backward digit span that a participant recalled correctly during all 14 trials.

Familiarity

When the answer to the question "Have you ever eaten this food?" will be 'yes', the food will be coded as familiar for a participant.

Liking

For each participant and each food a liking score from 0 to 100 will be recorded (anchors: not at all, extremely).

Health motivation in food choices

Both health and weight control motivation scores will be computed by averaging ratings for individual items in each dimension (health motivation: 6 items; weight control motivation: 4 items). They will range from 1 to 4: 1 = Not at all important; 2 = A little important; 3 = Moderately important; 4 = Very important. Cronbach's alpha will be calculated as an indicator of internal consistency in order to compare our data with the original study that developed this measure [24].

Other variables

BMI will be calculated as weight (kg) / height (m²). BMI data will be trimmed for implausible values excluding weight for less than 30 kg and more than 250 kg, height for less than 145 cm and more than 3m, BMI < 14 or BMI > 48 [33], [34].

Physical activity level will be estimated based on IPAQ-SF answers as MET-minutes per week²: self-reported physical activity in minutes*MET score [walking = 3.3, moderate intensity = 4.0, vigorous intensity = 8.0]*number of days [25].

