7.4. Familiarity and liking

We will report the percentage of dishes that participants are familiar with and the average liking score across foods overall and for participants of lower and higher education. Differences in familiarity between the two groups will be tested using Chi-square tests and differences in liking using t-tests.

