16. APPENDIX G: BASELINE QUESTIONNAIRE

1. *Gender*

- Male
- Female
- Other

2. *Age*

- __ (free text; range of 18-99)

3. *Ethnicity*

- White
- Black
- Asian
- Mixed
- Other

4. *What is your current employment status?*

- Full or part-time
- Student
- Retired
- Temporary or permanently sick or disabled
- Looking after home/family
- Other unemployed

5. *What is your highest educational qualification? If you are a student please select the diploma being studied for.*

- No qualification
- 1-3 GCSEs
- 4+ GCSEs
- A level
- CertHE
- DipHE
- Higher education or Bachelor's degree
- Post-Graduate degree
- Doctoral or professional degree

6. *After leaving school (i.e. at 16 years old), how many further years of higher education (i.e. a formal course) did you study for?*

Examples:

If you left school and did not go on to study further in higher education, your answer would be 0.

If you left school and then studied for two years for A levels, your answer would be 2.

If you completed A levels over two years and then also studied for a three-year undergraduate degree, your answer would be 5.

- __ (free text)

7. *What is your annual household income (after tax), including all earners in your household, in GBP (to the nearest £1000)?*

[figure not shown]
£_____ (free text; range 0-999,999)

8. How many adult(s) or child(ren) aged 14 and over live at your house, including you?
__ (free text; range of 1-20)

9. How many child(ren) aged under 14 live at your house, including you?
__ (free text; range of 1-20)

10. This is an attention check. How many times have you visited the planet Mars?
 Several times
 Just once
 Never

11. Think of a ladder (see the image below) as representing where people stand in society. At the top of the ladder are the people who are best off—those who have the most money, most education and the best jobs. At the bottom are the people who are worst off—who have the least money, least education and the worst jobs or no job. The higher up you are on this ladder, the closer you are to people at the very top and the lower you are, the closer you are to the bottom. Where would you place yourself on the ladder?

Choose the number whose position best represents where you would be on this ladder:

1 2 3 4 5 6 7 8 9 10

12. Are you currently dieting?
 Yes
 No

13. Weight

Select the unit:

- kg
- st and lb

— — —

14. Height

Select the unit:

- cm
- ft and in

— — —

15. *How hungry do you feel?*

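### The liking-adjusted sensitivity analysis conditions on a rating taken after the labels and the portion choice, so it need not estimate the total label effect and can report a misleading deviation.

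*Combined protocol and SAP*

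**What the plan says.** Section 7.6 (Sensitivity analyses) lists four variations on the main model. One is "including hunger and liking as covariates in the main model as these two variables are likely to influence how much one serves oneself". The section then commits to reporting departures from the main pattern of significance, defined as "any significant differences between conditions becoming not significant, and vice versa".

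Section 6 (Study flow) fixes the order of measurement: randomisation, baseline questionnaire, meal choice task, executive function tasks, health motivation, physical activity, and then the block headed "FAMILIARITY AND LIKING". No earlier liking rating is listed. Section 5.6 describes the rating: "Participants will be presented with the picture of the 600 kcal portion of each food". Section 7.1 adds: "For each participant and each food a liking score from 0 to 100 will be recorded".

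Hunger ("How hungry do you feel") is item 15 of the baseline questionnaire in Appendix G. It is asked after randomisation but before any label appears.

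Section 7.4 plans to report the "average liking score across foods overall and for participants of lower and higher education". It has no comparison by labelling arm.

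**The concern.** The reason given for adjusting treats liking purely as a cause of how much is served. The order of measurement allows two other routes. A label could change how a dish is rated later, which makes liking part of the pathway from label to portion. The portion a participant has just chosen could also colour the later rating, which makes liking partly a consequence of the outcome. In either case, conditioning on liking changes what the label coefficient estimates.

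The check is meant to show whether the label result is robust. If liking has moved, a change in significance may reflect the adjustment rather than any fragility in the result, yet the reporting rule treats the two alike. The planned tables would not let a reader tell them apart, because liking is not shown by arm. Hunger does not share the problem, but it enters the same model, so its contribution cannot be separated.

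**Working it through.** **1. Order of measurement**

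| Variable | Where measured | Before labels are seen? | Before portions are chosen? |
|---|---|---|---|
| Hunger | Appendix G, item 15 | Yes | Yes |
| Liking | Section 6, after the meal task, executive tasks and two questionnaires | No | No |

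Only hunger is a baseline covariate for the label contrast.

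**2. What the adjusted coefficient estimates**

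Adjusted effect = total effect − b × δ, where δ is the shift in mean liking due to arm and b is the fitted kcal per liking point. It equals the total effect only if δ = 0 (or b = 0).

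**3. Scale from the plan's own inputs (Section 7.9)**

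- SD 300 kcal at each level, 18 dishes, 400 per arm; alpha 0.05, taken as two-sided.
- Variance of a participant mean = 300² + 300²/18 = 90,000 + 5,000 = 95,000.
- SE of a contrast = √(95,000 × 2/400) = 21.8 kcal.
- Effect detectable at 80% power = (1.960 + 0.842) × 21.8 = 61.1 kcal.

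This matches the plan's 8% only if the control mean is 61.1/0.08 ≈ 763 kcal per dish. The documents give no control mean, so the sample-size figure can be neither confirmed nor refuted. I use 61 kcal only as a scale.

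**4. Label shift in liking only**

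Assumed, not in the documents: b = 3 kcal per point, liking SD 25. Power = Φ(effect/21.8 − 1.96).

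| Shift in liking | Adjusted effect (kcal) | Attenuation | Power | Change from 0.80 |
|---|---|---|---|---|
| 0 | −61.1 | 0% | 0.80 | 0 |
| −1 | −61.1 + 3 = −58.1 | 3/61.1 = 5% | 0.76 | −0.04 |
| −2 | −61.1 + 6 = −55.1 | 6/61.1 = 10% | 0.71 | −0.09 |
| −3 | −61.1 + 9 = −52.1 | 9/61.1 = 15% | 0.67 | −0.13 |
| +2 | −61.1 − 6 = −67.1 | inflated by 10% | 0.87 | +0.07 |

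The drop in power approximates how often a significant result turns non-significant. Simulations of a random-intercept model (two arms of 400, 18 dishes) agree. Over drops of 1 to 3 points, about 2% to 15% of runs flip, depending on the run and on how liking variance is split within and between people. With no shift, about 1% flip.

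At the stricter level that Section 7.5 gives as an example (0.05/12), a 10% attenuation takes power from 0.475 to 0.365.

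**5. Adding carry-back from the chosen portion**

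Let ratings move γ points per kcal served. The within-person slope becomes b = (3 × 625 + γ × 90,000)/(625 + 2γ × 3 × 625 + γ² × 90,000), and the arm shift in liking gains γ × 61.1 points.

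- γ = 0.01: b = 2,775/671.5 = 4.13. Removed: 4.13 × 0.61 = 2.5 kcal, or 4%.
- γ = 0.02: b = 3,675/736 = 4.99. Removed: 4.99 × 1.22 = 6.1 kcal, or 10%.
- γ = 0.02 with a 3-point drop: 4.99 × 4.22 = 21.1 kcal, or 35%.

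Carry-back also changes the standard error, so the power column in step 4 does not carry over. In one simulation (within-person liking SD 22, between-person 10), γ = 0.02 alone shrank the effect to about −54 kcal but flipped only 1.7% of runs, against 1.4% with neither path.

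**The case against.** The strongest reply is that the documents give no evidence that liking moves. The item asks about the food rather than the portion. Everyone sees the same 600 kcal picture, and people new to a dish are told to think of a similar one. The executive tasks alone take about 2.5 + 7 = 9.5 minutes between the portion task and the rating. Nothing is eaten, so carry-back could only be a rating artefact. A stable preference is plausible, and the bias would then be zero. This stands as an argument about size. It does not settle the matter, because the plan includes no by-arm comparison that would show whether liking stayed stable.

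It is also true that Section 7.6 only reports deviations and does not let a sensitivity result override the main one. That limits the harm to a misleading statement about robustness.

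A reader might infer more than the documents support:

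- **That the adjustment must remove part of the label effect.** The direction depends on which way labels move liking, and the documents do not say.
- **That attenuation of 30% or more is to be expected.** That needs a 3-point drop stacked with the larger carry-back, and both are assumed.
- **That adjusting for liking gains little precision.** Averaging over 18 dishes deals only with the 5,000 within-person part of 95,000. Liking could explain some of the 90,000 between people.
- **That the dish-exclusion check has the same flaw.** It also uses post-label liking, but it drops the same dishes in every arm, so it does not adjust the arm contrast in this way.

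**Conclusion.** The point holds in a limited form. The order of measurement is plain from the study flow. Section 7.6 adjusts a randomised contrast for a variable recorded after both exposure and outcome, so that check need not target the total label effect. If labels or portion choice move liking, the result is distorted in a direction the plan cannot foresee, and the deviation rule may report it as non-robustness or as a newly significant difference.

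The size is unknown. On illustrative inputs (61 kcal effect, 3 kcal per point, liking SD 25), a drop of 1 to 3 points gives 5% to 15% attenuation and about 2% to 15% of runs losing significance. A 2-point rise would inflate the effect to about −67 kcal. With no movement in liking there is no bias.

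It would be wrong to infer that the primary result is at risk: the main model in Section 7.5 contains no liking term. One of four sensitivity analyses is affected, and only through its liking component.

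**What to change.** In Section 7.6, split the bullet and use baseline hunger alone as the covariate check on the label effect. In Section 7.4, add liking by labelling arm, either as means or with the same mixed model using liking as the outcome. If a liking-adjusted model is kept, describe it as adjusted for a post-exposure variable and exempt it from the deviation rule.

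The cost is a few lines of SAP text and, at most, one extra model on data already being collected. The downside is that the covariate check no longer adjusts for chance imbalance in true liking, or for between-person variance that liking explains. With about 400 randomised per arm, this loss is minor.

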7. STATISTICAL ANALYSES

All statistical analyses will be performed using SAS version 9.3 (SAS Institute, Inc., 2012 SAS® 9.3. Cary, NC). The level of significance will be set at $p < 0.05$ for the main and sensitivity analyses, $p < 0.01$ for secondary analyses and $p < 0.001$ for exploratory analyses unless otherwise specified. Linear mixed models will be fitted with PROC MIXED.

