7.5. Main analyses

The primary aim of the statistical analyses will be to test the effect the labelling intervention and SEP on self-served energy. Secondary analyses will be run in order to investigate the role of potential mediators to explain the relationship SEP-self-served energy. The measure of SEP used in our main analyses will be the *highest educational qualification* (binary variable: *lower vs. higher*) because previous research showed that people of higher education were more likely to use nutrition labels [35], [36].

² MET-minutes: Metabolic Equivalent of Task of an activity × minutes performed.

Linear mixed effect models will be run in order to test the effect of the labels and of highest educational qualification on the self-served energy, with participants and dishes set as random effects to account for correlation between repeated measures by the same participant and across the different food items. The main model will test the effect of the labelling intervention (four levels: kcal labelling, PACE labelling, kcal and PACE labelling, no labelling), highest educational qualification (two levels: lower, higher) and the interaction between labelling intervention and highest educational qualification. If the interaction is significant, analyses will be stratified by *highest educational qualification (lower and higher)* and two linear mixed models will be fitted to examine the effect of the labelling intervention on self-served energy.

If there is a main effect of the labelling intervention in one of the above linear mixed models we will follow up this main effect by conducting the following pairwise comparisons:

- Self-served energy in each of the three labelling conditions compared to no labelling condition:
 - o No labelling vs. kcal labelling
 - o No labelling vs. PACE labelling
 - o No labelling vs. kcal and PACE labelling combined
- Self-served energy in the combined labelling condition compared to single labelling conditions
 - o Kcal and PACE labelling combined vs. kcal labelling
 - o Kcal and PACE labelling combined vs. PACE labelling
- Self-served energy in one single labelling condition compared to the other single labelling condition:
 - o Kcal labelling vs. PACE labelling

We will apply a Bonferroni correction to the level of significance based on the number of pairwise comparisons made (e.g., 12 comparisons: $0.05/12=0.004$).

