7.9. Sample size

A meta-analysis of six studies investigating the impact of kcal labelling on energy consumed from a single food did not demonstrate a statistically significant effect [11]. However the designs of these studies were different from the present study: the food options were mainly snacks (only one study offered to consume main meals [38]) and participants were not aware of the amount of kcal they actually consumed (the label was placed on the container or packaging, adjacent to the food, or presented on a display board). In our design, we expect a significant effect of kcal labelling with a reduction of 8.4% of self-served energy per meal may occur, which is the effect size found in a meta-analysis investigating the impact of kcal labelling on energy consumed during a meal with a range of available food options – i.e., the most similar design to the present study. The most up to date evidence of an effect of PACE labelling on energy consumed from foods/drinks is a meta-analysis of two studies and showed a significant reduction of 14.4%. Due to the small number of participants included in this meta-analysis, we conservatively powered our study to be able to detect an 8% reduction for both type of labels (kcal, PACE or kcal and PACE).

We will run a two-level mixed model including 18 trials (level 1) per participant (level 2) and compare self-served energy in each of the four trial arms (control, kcal labelling, PACE labelling, kcal and PACE labelling). We estimate SD of 300 kcal for self-served energy at level 1 and level 2 based on average SD of energy consumed during experimental meals [11]. A sample size of 1,600 participants with $\alpha = 0.05$ will allow to detect a 8% energy reduction between any of the four groups at power = 0.80. It will also allow to detect a small effect ($f=0.07$) of the interaction between the interventions and higher educational qualification education at power = 0.80 (MLPowSim) [39].

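### The sensitivity analyses define a deviation only as a change in significance status, which cannot separate lost precision from a changed effect

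*Combined protocol and SAP*

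**What the plan says.** Section 7.6 lists four sensitivity analyses:

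- excluding aim guessers, or adding aim guessing as a covariate "if more than 20% of participants guess the aim of the study";
- replacing binary education with the composite education score;
- adding hunger and liking as covariates;
- excluding unfamiliar or poorly liked dishes.

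The section opens by asking whether the pattern of results differs. Its closing sentence narrows that question: "We will report whether sensitivity analyses result in deviations from the pattern of significance to the main analyses", explained in brackets as "any significant differences between conditions becoming not significant, and vice versa".

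On thresholds, the opening of Section 7 states "The level of significance will be set at $p < 0.05$ for the main and sensitivity analyses". Section 7.5 adds, for the pairwise follow-up, a "Bonferroni correction to the level of significance based on the number of pairwise comparisons made", with 0.05/12 = 0.004 as its example. Section 7.6 does not restate the correction; I assume it carries over.

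The analysis plan mentions confidence intervals only for the moderated mediation in Section 7.7. No section plans estimates, intervals or a tolerated change for the sensitivity analyses.

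**The concern.** A sensitivity analysis should show whether the effect changes when an assumption or a subset changes. Significance status mixes the size of the estimate with its precision. Excluding aim guessers reduces the sample, so a contrast near its threshold can lose significance although labelling works just as well in those who remain. In the other direction, a strong contrast can shrink a great deal and still pass, and a non-significant contrast can change sign without being counted.

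The rule covers all four analyses and 6 pairwise contrasts, or 12 if the models are stratified by education. At stake is the reader's ability to tell, most of all for the aim-guesser check, whether a reported deviation means a different effect or only fewer participants.

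**Working it through.** **Inputs from the documents**

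- Section 7.9: "We estimate SD of 300 kcal for self-served energy at level 1 and level 2"; a "two-level mixed model including 18 trials (level 1) per participant (level 2"); 1,600 participants, 400 per arm.
- Section 7.9: this sample "will allow to detect a 8% energy reduction between any of the four groups at power = 0.80", at alpha 0.05.
- Section 7.5: six pairwise contrasts in one model (0.05/6 = 0.0083, critical z 2.64), or twelve over two education strata (0.05/12 = 0.0042, critical z 2.87).
- Section 7.6: at most 20% of participants excluded as aim guessers.

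**Assumptions.** Tests are two-sided. Exclusions are at random and equal across arms. Dish effects cancel between arms. The plan gives no expected share of aim guessers, so I show 10% and 20%.

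**1. The plan's own power figure**

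- Variance of a participant mean: 300² + 300²/18 = 95,000; SD 308.2 kcal.
- SE of an arm difference: 308.2 × √(2/400) = 21.8 kcal.
- 80% power at 0.05 needs z = 1.96 + 0.84 = 2.80, or about 61 kcal.
- 61 kcal is 8% of about 763 kcal. The control mean is not stated, so the claimed power cannot be confirmed. The status-change rates below need only z = 2.80, which follows from the stated 80% power.

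**2. The same estimate, a different verdict**

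An estimate of 61 kcal with 400 per arm has z = 61/21.8 = 2.80 and passes 0.05/6. With 20% dropped (320 per arm) the SE is 308.2 × √(2/320) = 24.4 kcal, so z = 61/24.4 = 2.50, which fails. A deviation is reported although the estimate has not moved.

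**3. How often status changes when the true effect does not**

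With a share d dropped, the full-sample and subset z statistics are bivariate normal, with means 2.80 and 2.80√(1−d) and correlation √(1−d). If the estimate is held identical, status changes only when the full-sample z lies between c and c/√(1−d), where c is the critical value.

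| Threshold | Dropped | Loses significance | Gains significance | Any change | Estimate held identical |
|---|---|---|---|---|---|
| 0.05/6 | 10% | 0.084 | 0.027 | 0.11 | 0.057 |
| 0.05/6 | 20% | 0.147 | 0.029 | 0.18 | 0.124 |
| 0.05/12 | 10% | 0.084 | 0.027 | 0.11 | 0.061 |
| 0.05/12 | 20% | 0.144 | 0.029 | 0.17 | 0.131 |

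In a simulation where all three labels have the design effect, the chance that at least one of six contrasts changes status at 0.05/6 is 0.30 with 10% dropped and 0.43 with 20% dropped.

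The 0.05/12 rows keep z = 2.80 as a benchmark. Twelve contrasts arise only after stratification, with about 200 per arm in each stratum. There the SE is 308.2 × √(2/200) = 30.8 kcal, and 61 kcal gives z = 1.98. The same formula then gives any-change rates of about 0.07 (10% dropped) and 0.10 (20% dropped).

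**4. Changes that the rule misses**

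- Suppose adjustment for hunger and liking halves an effect from 122 to 61 kcal at the same SE of 21.8 kcal. Then z falls from 5.6 to 2.8 (p = 0.0051). This is still significant at 0.0083, so no deviation is reported. It is not significant at 0.0042, so a deviation is reported there.
- At 0.05/6 the critical difference is 2.64 × 21.8 ≈ 57.5 kcal. An estimate could move from −57 to +57 kcal and stay non-significant throughout.

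**5. Excluding dishes**

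With 4 of 18 dishes removed, the variance is 90,000 + 90,000/14 = 96,429. The SE rises by √(96,429/95,000) − 1 = 0.7%.

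**The case against.** The strongest reply is that the closing sentence of Section 7.6 is a minimum reporting commitment. Estimates are not excluded, the stated aim is the pattern of results, and a significance rule is at least objective and fixed in advance. The first part stands: a reader might infer that the plan forbids estimates, or that the study's conclusion must rest on this criterion, and the text says neither. But a change of status is the only definition of a deviation that it gives.

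Four further limits also stand.

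- A reader might infer that false deviations will occur. The rates show that they can, in a minority of trials for any one contrast.
- Only the aim-guesser analysis removes participants, and by at most 20%. Two analyses change covariates or the education measure. The dish exclusion removes trials, at almost no cost in precision.
- Part of the 17–18% comes from estimates that move by chance when participants are removed. The narrower case of an unmoved estimate gives 12–13%.
- The halved-effect example works at 0.05/6 only and assumes an unchanged SE. Exclusion of aim guessers is a less likely route to halving: if 20% are dropped and the rest show half the overall effect, the excluded would need (1 − 0.8 × 0.5)/0.2 = 3 times the overall effect.

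Finally, a comparison in kcal or per cent is not available everywhere. The composite education score is z-scored, so its interaction is on a different scale from that for binary education.

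**Conclusion.** The point holds in limited form. Section 7.6 uses a criterion that cannot separate lost precision from a changed effect. At the design effect, with exclusions at random and balanced across arms, a contrast changes status in about 11% of trials with 10% dropped and 17–18% with 20% dropped, although the true effect is the same. With an identical estimate the figures are about 6% and 12–13%. In the other direction, a halved effect can go unreported at 0.05/6 but not at 0.05/12.

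The documents do not support the stronger reading that all four analyses are prone to false deviations through lost information: that mechanism matters for the aim-guesser exclusion and is negligible for the dishes. No primary test, sample size or primary conclusion changes. This is a worthwhile improvement in reporting, not a flaw that threatens the trial.

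**What to change.** Replace the last sentence of Section 7.6 with:

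> For each sensitivity analysis we will report the labelling contrasts (kcal, with confidence intervals) beside the main-analysis estimates, and the interaction where it is on the same scale; robustness will be described primarily by the change in the estimate and its confidence interval, with any change in significance status reported as secondary information. For the composite education score, which is on a different scale, the interaction will be reported descriptively with its confidence interval.

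The cost is a slightly larger results table and a less mechanical criterion, since the wording sets no numerical tolerance. The models are already planned, and no new data are needed.
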